5.2.2 Extrapyramidal Symptom Rating Scale–Abbreviated (ESRS-A)

The ESRS-A is assessed at Baseline, Weeks 2, 4, 8, 12, 16, 28, 40, and 52 (EOT/ET). The ESRS was developed to assess drug induced movement disorders such as parkinsonism, akathisia, dystonia and tardive dyskinesia with established reliability, validity, and sensitivity. The ESRS-A, an accepted modified form of the original ESRS, is used during the study to monitor for any worsening in extrapyramidal symptoms or signs at scheduled and

unscheduled visits. The CGI-S for each movement subtype (i.e., parkinsonism, dystonia, dyskinesia, and akathisia) rates the severity of a subject's movement disorder and the CGI-S score for each movement subtype ranges from 0 to 5:

0 = Absent	1 = Minimal	2 = Mild
3 = Moderate	4 = Severe	5 = Extreme

Higher CGI-S scores denote more severe movement disorder. Missing scores will not be imputed.

5.2.3 Changes in Sexual Functioning Questionnaire Short Form (CSFQ-14)

The CSFQ-14 is assessed at Baseline, Weeks 2, 4, 8, 12, 16, 28, 40, and 52 (EOT/ET). The CSFQ-14 is a 14-item version of the CSFQ. This is a patient-facing questionnaire, with a male version and a female version. The total score ranging from 14 to 70 will be calculated as the sum of the scores for all 14 items. Higher total scores denote better sexual functioning. Missing item scores will be imputed using the arithmetic mean of the non-missing item scores and rounded to the nearest integer. The total score will be considered as missing if there are missing scores for 3 or more items.

5.2.4 Clinical Global Impressions Scale – Severity (CGI-S)

The CGI-S is assessed at Baseline, Weeks 2, 4, 8, 12, 16, 28, 40, and 52 (EOT/ET). The CGI-S is the scale used by the Investigator or designee to rate the severity of the disorder. The CGI-S rates the severity of a subject's depression over the past 7 days and the CGI-S score ranges from 1 to 7:

1 = Normal, not at all ill	5 = Markedly ill
2 = Borderline mentally ill	6 = Severely ill
3 = Mildly ill	7 = Among the most extremely ill patients
4 = Moderately ill	

Higher CGI-S scores denote more severe depression. Missing CGI-S scores will not be imputed.

5.2.5 Hamilton Rating Scale for Depression – 17 Items

The HAMD-17 is assessed at Baseline, Weeks 2, 4, 8, 12, 16, 28, 40, and 52 (EOT/ET). The HAMD-17 consists of 8 items with a score on a 3 point scale and 9 items with a score on a 5 point scale. The total score ranging from 0 to 52 will be calculated as the sum of the scores

for all 17 items. Higher total scores denote more severe depression. Missing item scores will be imputed and rounded to the nearest integer as follows:

- Missing scores for items with a score on a 3 point scale will be imputed using the arithmetic mean of the non-missing scores for items with a score on a 3 point scale
- Missing scores for items with a score on a 5 point scale will be imputed using the arithmetic mean of the non-missing scores for items with a score on a 5 point scale

The total score will be considered as missing if there are missing scores for 4 or more items.

5.2.6 Sheehan Disability Scale (SDS)

The SDS is assessed at Baseline, Weeks 4, 12, 28, and 52 (EOT/ET). The SDS is a 3-item subject-facing questionnaire used to evaluate impairments in the domains of work, social life/leisure, and family life/home responsibility. Subjects rate each item using an 11-point scale ranging from 0 (not at all) to 10 (extremely).

The primary analysis will be performed on the mean score ranging from 0 to 10 calculated as the arithmetic mean of the scores for all 3 items and rounded to the nearest 2 decimal places. Higher mean scores denote greater disability. If a subject indicates that no work/school occurred, the mean score will be calculated as the arithmetic mean of the other two item responses (Social Life and Family Life/Home Responsibilities) and rounded to the nearest 2 decimal places. If either of the other two item responses is missing, or if the work/school response is missing and the subject does not indicate that no work/school occurred, the mean score will be missing.

5.2.7 Karolinska Sleepiness Scale (KSS)

The KSS is assessed at Baseline, Weeks 2, 4, 8, 12, 16, 28, 40, and 52 (EOT/ET). The KSS is a scale that measures the subject's drowsiness and is frequently used in studies measuring subjective sleepiness. Scoring is based on a 9-point verbally anchored scale going from "1 = extremely alert" to "9 = very sleepy, great effort to keep awake, fighting sleep". Higher scores denote more drowsiness. Missing scores will not be imputed.

5.3 Analysis Visit Windows

In general, the open-label Baseline assessment will be defined as the last non-missing assessment, including those from repeated and unscheduled measurements, before or on the first open-label dose date. Exceptions to this definition will be handled on a case by case basis.

Efficacy and safety assessments will be summarized by analysis visit as presented in Table 1 below.

Table 1 Analysis Visit Windows

Open-label (OL) Analysis Visit Name	Target Study Day¹	Study Day Interval
OL Baseline	1	≤1 (based on the first OL dose date)
OL Week 2	15	2 to 21
OL Week 4	29	22 to 42
OL Week 8	57	43 to 70
OL Week 12	85	71 to 98
OL Week 16	113	99 to 154
OL Week 28	197	155 to 238
OL Week 40	281	239 to 322
OL Week 52	365	323 to 379
OL Follow-up	395	380 – maximum

¹ If the assessment date ≥ first OL dose date, study day = assessment date - first OL dose date + 1, otherwise study day = assessment date – first OL dose. Study day 1 is the first OL dose date.

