## 4.2 Exclusion Criteria

A subject must meet none of the following exclusion criteria to be eligible for the study.

1. Is judged by the Investigator or the Medical Monitor to be inappropriate for the study, due to AEs, medical condition, or noncompliance with investigational product or study procedures in Study ACP-103-054 or Study ACP-103-059, or is judged to be a danger to self or others
2. Has any of the following electrocardiogram (ECG) results at Baseline (i.e., Week 6/ EOT visit of Study ACP-103-054 or Study ACP-103-059):
  - a. If the subject is **not** on citalopram, escitalopram, or venlafaxine (immediate or extended release):
    - i. QTcF >450 ms, if QRS duration <120 ms
    - ii. QTcF >470 ms, if QRS duration  $\geq$ 120 ms
  - b. If the subject is on citalopram, escitalopram, or venlafaxine (immediate or extended release):
    - i. QTcF >425 ms, if QRS duration <120 ms
    - ii. QTcF >450 ms, if QRS duration  $\geq$ 120 ms
3. Has a heart rate (as measured by peripheral pulse rate) <50 beats per minute at Baseline (i.e., the Week 6/EOT visit of Study ACP-103-054 or Study ACP-103-059) not explained by regular exercise or medication, in discussion with the Medical Monitor

4. Has a body mass index (BMI)  $<18.5 \text{ kg/m}^2$  or known unintentional clinically significant weight change (i.e.,  $\pm \geq 7\%$  of body weight) in Study ACP-103-054 or Study ACP-103-059 as assessed by the Investigator
5. Has clinically significant laboratory abnormalities that, in the judgment of the Investigator or Medical Monitor, would either:
  - a. jeopardize the safe participation of the subject in the study; OR
  - b. would interfere with the conduct or interpretation of safety or efficacy evaluations in the study
6. Is suicidal as defined below at Visit 1 (Baseline) of the present study:
  - a. An answer of “yes” to C-SSRS questions 4 or 5 (current or over the last 6 months); OR
  - b. Has attempted suicide within 1 year prior to Visit 1 (Baseline); OR
  - c. Is actively suicidal in the Investigator’s judgment
7. Has developed delirium or a neurologic, cardiovascular, respiratory, gastrointestinal, renal, hepatic, hematologic, or other medical or mental disorder, including cancer or malignancies that, in the judgment of the Investigator or the Medical Monitor, would increase the risk associated with taking study medication or significantly interfere with the conduct or interpretation of the study

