### **6.3.4 Electrocardiograms**

All 12-lead electrocardiograms (ECGs) will be complete, standardized recordings. A single 12-lead ECG will be completed at all scheduled visits at the investigator site during the present study (Table S-1). In the US and UK, a 6-lead ECG device will be given to subjects in order to perform ECGs on themselves at home when they cannot go the clinic and site staff cannot go to their home. This should be done in discussion with the Medical Monitor. When an ECG is performed outside of the investigator site, this should be documented in the source record. All ECGs will be centrally read; the interpretation by the central cardiologist is considered the official result. If a site performs additional ECGs beyond the single ECG prescribed at Baseline, the mean QTcF/QRS values of all the tracings of adequate quality will be used to determine eligibility.

At Baseline, a subject may be enrolled based on the machine read of the locally completed ECG. If the interpretation of the ECG by the central cardiologist returned after enrollment indicates QTcF outside of the allowable range, the subject will be discontinued from the study, but this will not be considered a protocol deviation.

Electrocardiograms should be performed before blood sampling or at least 30 minutes after blood sampling. The subject must rest in a supine position for 5 minutes before the ECG is obtained. ECG tracings (paper or electronic) will be reviewed and interpreted by a qualified clinician. ECG tracings and results (ventricular rate, PR, QRS, QT, QTcF and QTcB intervals) will be included and summarized in the subject's study records.

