14.4 Electrocardiogram (ECG)

All tracings will be evaluated by qualified clinicians. At the Baseline visit, the machine-read results will also be recorded. All data, including the machine-read Baseline results, will be listed.

Observed values of ECG variables (heart rate, PR interval, RR interval, QRS interval, QT interval, and QTc intervals) and the changes from Baseline at scheduled visits will be summarized.

QTc intervals include QTcB (Bazett’s formula) and QTcF (Fridericia’s formula). QTcF will also be categorized into the following categories (msec) and the number and percentage of subjects in each category will be summarized at scheduled visits and overall post-baseline maximum:

- Observed: ≤450, 451 - ≤480, 481 - ≤500, and >500; >450; >480.
- Change from Baseline: ≤10, 11 - 30, 31 - 60, and >60; >30.

The above summaries will also be presented for the following subgroups: subjects with background antidepressant of citalopram, subjects with background antidepressant of escitalopram, and subjects with background antidepressant of venlafaxine.

For cardiologist’s interpretations, the number and percentage of subjects with ECG results

that are determined as normal or abnormal will be summarized at scheduled visits. The overall post-baseline worst interpretation will also be summarized (i.e. if a subject has one or more ECG results that is/are considered as abnormal, this subject will be counted in the abnormal category). Cardiologist’s interpretations will also be summarized in a shift table to determine the number and percentage of subjects with ECG results classified as normal or abnormal at scheduled post-Baseline visits relative to the same classification at the Baseline visit. The shifts from Baseline to overall post-Baseline worst interpretation will also be presented. For the by-visit shift summary, the denominator is the number of subjects with non-missing cardiologist’s interpretation at Baseline and the given visit. For the summaries of shift from Baseline to the overall post-Baseline worst interpretation, the denominator is the number of subjects with non-missing Baseline and at least 1 post-Baseline cardiologist’s interpretation.

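### Repeat Baseline ECGs are averaged for eligibility but reduced to the last tracing for analysis; if repeats follow a failing reading, QTcF change is inflated in a small subgroup

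*SAP*

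**What the plan says.** Protocol 6.3.4 plans one ECG per visit: "A single 12-lead ECG will be completed at all scheduled visits at the investigator site during the present study". It foresees extras at Baseline, and for those says that "the mean QTcF/QRS values of all the tracings of adequate quality will be used to determine eligibility". With QRS below 120 ms, the exclusion limits in Protocol 4.2 are "QTcF >450 ms, if QRS duration <120 ms" for subjects not on citalopram, escitalopram or venlafaxine, and "QTcF >425 ms, if QRS duration <120 ms" for subjects on one of them.

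SAP 5.3 defines open-label Baseline, in general, as "the last non-missing assessment, including those from repeated and unscheduled measurements, before or on the first open-label dose date". It adds: "Exceptions to this definition will be handled on a case by case basis". SAP 14.4 summarises QTcF change at each visit and, by category, at the post-Baseline maximum as well ("Change from Baseline: ≤10, 11 - 30, 31 - 60, and >60; >30"). It repeats these summaries for citalopram, escitalopram and venlafaxine users. It gives no Baseline rule of its own and no averaging. SAP 5.3.2 also selects a single assessment per window.

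**The concern.** One subject can have two Baseline QTcF values from the same visit: the mean that admitted the subject and the last tracing from which change is measured. The difference need not be random. With one ECG planned and the averaging rule tied to eligibility, a plausible reason for a repeat is a first reading above the limit. If tracings are added until the mean passes, the last one is selected to be low, and ordinary regression to the mean then looks like a QTcF increase on drug.

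Protocol 1.3 acknowledges that pimavanserin lengthens QT, by about 5-8 ms on average. An artefact of similar size in subjects near the limits bears on the change-from-Baseline tables, most of all in the three antidepressant subgroups, where the stricter limit applies.

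**Working it through.** The documents give no figure on this point, so there is none to reproduce.

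**1. Direction.** Let m(n) be the mean of the first n tracings, x(n) the last of them and L the limit. Since n·m(n) = (n−1)·m(n−1) + x(n),

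x(n) − m(n) = (n−1)·[m(n) − m(n−1)].

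If repeats stop as soon as the mean qualifies, then m(n−1) > L ≥ m(n), so the last tracing is always below the mean. Example with L = 450: readings 458 and 440 have mean 449; the SAP Baseline is 440, which is 9 ms lower.

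Without that stopping rule the sign is not fixed:
- 444 then 452: mean 448, last 452, 4 ms higher.
- A fixed set of 456, 440, 452: mean 449.3, last 452, 2.7 ms higher.

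**2. Size under the stopping rule (simulation).** Inputs from the documents: limits 450 and 425 ms (QRS <120 ms), the mean rule for eligibility and the last-tracing rule for analysis. Assumptions not in the documents: population mean QTcF 400-420 ms, between-subject SD 15-20 ms, within-subject SD 6-10 ms, every failing reading repeated, at most three tracings, no true drug change. Tracing = true value + independent error. Over 36 settings, among subjects who qualified on repeats:

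| | 450 limit | 425 limit |
|---|---|---|
| Share of eligible subjects | 0.1-4% | 2-13% |
| Mean of tracings minus true value | about +1 to +7 ms | about 0 to +3 ms |

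Across both limits the last tracing averaged about 3 to 9 ms below the true value. The expected false increase at any later visit is the same amount. Root-mean-square error was lower for the mean than for the last tracing in 35 of 36 settings.

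**3. Categories.** On the post-Baseline maximum over the eight scheduled visits, false changes >30 ms at the 425 limit occurred in 0.5-26% of these subjects with the last tracing and 0-4% with the mean. The study was stopped early (SAP 3.5, 3.6), so subjects with fewer visits have less opportunity for this. At a single visit, with a fixed two or three tracings and population mean 405 or 415, the figures were 0-3.7% against 0-0.3% at 450, and 0.1-5.0% against 0-0.6% at 425. False changes >60 ms were about 0%.

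**4. Dilution.** Shift in the overall mean change = share × (mean − last). At the top of the ranges (population mean 420):
- 450: 0.04 × (7.3 + 2.6) = 0.04 × 9.9 ≈ 0.4 ms. If all of the planned 420 subjects faced this limit, at most 420 × 0.04 ≈ 17 would be affected.
- 425: 0.13 × (9.2 + 0.2) = 0.13 × 9.4 ≈ 1.2 ms, among users of the three antidepressants only. Their number is not given.

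**5. Repeats with no trigger.** With routine triplicates, last minus mean averaged 0.0 ms. Changes >30 ms rose from about 0.5% with the mean to 1.7-2.0% with the last tracing, through noise alone.

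**6. Category gaps.** Means are not whole numbers. A later value of 460 against a mean Baseline of 449.3 gives a change of 10.7 ms, which fits neither ≤10 nor 11-30.

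**The case against.** The strongest reply is that there is no contradiction. The protocol confines the mean to eligibility, an analysis Baseline may properly differ, the SAP rule holds only in general, and SAP 5.3.2 refers to a programming document that is not available here. Each of these is true. But an exception left to case-by-case judgement in an open-label study is not prespecified, and nothing visible tells the programmer how to treat repeat ECGs.

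A reader might infer that every subject who qualified on repeats has a Baseline that is too low. The documents do not support this: they state neither a trigger nor a number of repeats nor a stopping rule, and without a trigger there is no directional bias. Enrolment may also rest on the local machine read while the central read is official, so selection and analysis may use different readings.

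A reader might also infer that the QTc PCI counts are inflated. Table 5 of the SAP uses observed values >500 ms, which need no Baseline, and changes >60 ms, which the artefact almost never produces. Nor can a last tracing above the limit arise under the assumed stopping rule; it needs a fixed number of tracings, which the protocol does not plan.

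The objection with most force is that averaging is not neutral. The mean includes the high first reading. At the 450 limit with SDs of 15 and 10 ms, its bias is +7.4 ms (population mean 400) and +5.9 ms (410), against −4.1 and −4.9 ms for the last tracing. Averaging can therefore understate an increase, and this must be stated alongside the remedy.

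**Conclusion.** The point holds in conditional form and is minor. That the two rules differ, and that no ECG exception is written, is certain from the text. The upward bias in QTcF change depends on repeats being prompted by a failing reading and ending once the mean qualifies, which is reasonable but inferred. Its size depends wholly on the assumed means and SDs. Subjects with QRS ≥120 ms, who face other limits, were not modelled.

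The reach is QTcF change from open-label Baseline, and its >30 ms category, in a small subgroup. That subgroup is proportionally larger among citalopram, escitalopram and venlafaxine users. The >60 ms and PCI counts, the post-Baseline observed-value categories and the exploratory change from the antecedent-study Baseline are essentially unaffected. No hypothesis test is planned, so no inference is at risk.

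**What to change.** In SAP 5.3, with a cross-reference in 14.4, define the Baseline for each ECG parameter as the mean of all adequate-quality, centrally read tracings at the Baseline visit. Write the QTcF categories without gaps: observed ≤450, >450 to ≤480, >480 to ≤500, >500; change ≤10, >10 to ≤30, >30 to ≤60, >60.

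State in the SAP that after a high first reading this mean tends to be too high and so can understate an increase. Add a sensitivity summary of QTcF change, overall and in the three antidepressant subgroups, that excludes or flags subjects with more than one Baseline ECG, and report how many there are.

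The cost is a few SAP sentences and a small programming change. No new data are needed, since Protocol 6.3.4 already has all ECGs read centrally, and the Baseline does not change for subjects with one tracing.

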5.3.1 Unscheduled Assessments

Both scheduled and unscheduled assessments, including early termination visits and remote visits, will be considered for planned timepoint summaries. All assessments will be presented in data listings.

5.3.2 Multiple Measurements within Visit Windows

If more than one assessment falls within a given window then the assessment closest to the target study day will be selected for the by-visit summaries. If two assessments are equidistant from the target day then the chronologically last assessment will be used for summary. Exceptions may be made for incomplete assessments, in which case, more complete assessments may be given priority. Details are provided in a separate programming conventions document.

For safety summaries where the most extreme values should be selected, e.g. overall post-baseline minimum, overall post-baseline maximum, and potentially clinically important values for overall post-Baseline summaries, all non-missing post-Baseline values should be considered, regardless of whether the value is selected for the by-visit summaries. All results will be presented in data listings.

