3.6 Coronavirus Disease 2019

In March, 2020, the emerging coronavirus disease 2019 (COVID-19) pandemic resulted in implementation of urgent safety measures designed to ensure subject safety. Mechanisms to record information on the potential impact of the COVID-19 pandemic on data itself, as well as data collection and integrity, were implemented (as detailed in the “Guidance for Site Documentation and Data Management Querying of Data Impacted by COVID-19” [GSD] in the Data Management Plan).

Screening and enrollment into studies ACP-103-054 and ACP-103-059 were closed and enrollment into ACP-103-055 was allowed to continue. The impact of COVID-19 on the statistical analysis is discussed in each of the relevant sections of this SAP.

Subjects who remained in this study who could not attend clinic visits were allowed to participate in remote visits via telephone or video, or site staff conducted the visit in a subject’s home. Sites were required to document details of all visits that are administered remotely.

Afterwards, ACP-103-055 was stopped early and the remaining subjects were discontinued in the study.

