13 METHODS OF EFFICACY ANALYSES

Descriptive statistics for all efficacy endpoints listed in [Section 12.1](#) including treatment responder and remission rates will be tabulated by the double-blind treatment group in the antecedent studies at scheduled timepoints. The summaries of the change from Baseline results will be presented in two ways (main analysis and exploratory analysis) as specified in [Section 5.1](#).

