Clinical laboratory values reported as continuous values for hematology, chemistry and urinalysis will be summarized using descriptive statistics at Baseline and scheduled post-Baseline visits. The change from Baseline values will also be summarized at scheduled post-Baseline visits. The overall minimum, maximum and last post-Baseline observed and change from Baseline values will also be summarized. For hemoglobin, hematocrit and uric acid, the above summaries will be presented for each gender as well as for both genders combined. For urinalysis with categorical results, the number and percentage of subjects will be tabulated by category at Baseline and scheduled post-Baseline visits, and the denominator is the number of subjects with non-missing values for the given parameter and visit. For glucose and lipid panel, the summary table will also be presented by fasting status (fasting vs. non-fasting).

Laboratory values will also be summarized in shift tables to determine the number and percentage of subjects with values classified as below (low), within (normal), or above (high) normal ranges at scheduled post-Baseline visits relative to the same classification at the Baseline visit. The shifts from Baseline to overall post-Baseline minimum and overall post-Baseline maximum will also be presented. For the by-visit shift summary, the denominator is the number of subjects with non-missing values at Baseline and the given visit for the given

parameter. For the summaries of shift from Baseline to the overall post-Baseline minimum or maximum, the denominator is the number of subjects with non-missing Baseline and at least 1 post-Baseline value for the given parameter. For hemoglobin, hematocrit and uric acid, the shift summaries will be presented for each gender as well as for both genders combined. For glucose and lipid panel, the shift table will be presented by fasting status (fasting vs. non-fasting).

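### An early-termination efficacy rating enters no efficacy table the SAP plans when an earlier scheduled rating in the same visit window is strictly closer to target; a last-assessment row would capture it

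*SAP*

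**What the plan says.** - **Who competes.** SAP 5.3.1: "Both scheduled and unscheduled assessments, including early termination visits and remote visits, will be considered for planned timepoint summaries". SAP 5.3: "Efficacy and safety assessments will be summarized by analysis visit as presented in Table 1 below".
- **Who wins.** SAP 5.3.2: when a window holds more than one assessment, "the assessment closest to the target study day will be selected for the by-visit summaries". On ties: "If two assessments are equidistant from the target day then the chronologically last assessment will be used for summary". There is one discretionary exception: "Exceptions may be made for incomplete assessments, in which case, more complete assessments may be given priority".
- **What efficacy tables exist.** SAP 13: descriptive statistics for all efficacy endpoints, including response and remission, "will be tabulated by the double-blind treatment group in the antecedent studies at scheduled timepoints". Neither SAP 12 nor SAP 13 plans a last-visit or endpoint summary. SAP 12.3 does not impute derived scores that are missing.
- **What other data get.** In SAP 5.3.2, safety summaries of extreme values draw on all post-Baseline values, selected or not. SAP 14.2 adds for laboratory values: "The overall minimum, maximum and last post-Baseline observed and change from Baseline values will also be summarized".
- **Context.** SAP 3.6: "ACP-103-055 was stopped early and the remaining subjects were discontinued in the study".

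**The concern.** The later Table 1 windows run well past their targets: Week 16 is day 113 in 99–154, Week 28 is day 197 in 155–238, and Week 40 is day 281 in 239–322. A subject can complete a scheduled visit near target and then stop weeks later in the same window. Both ratings are collected, but only the one nearer to target is summarised, and that is usually the earlier one.

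This differs from a missing rating. The final rating was made, and the selection rule leaves it out. It matters more here because the study was stopped and the remaining subjects were discontinued, so for them an ET rating may be the last observed status. Lack of efficacy is also a listed discontinuation reason (protocol 4.4). When such a subject leaves after worsening, the table keeps the earlier score and the subject is absent from the next row.

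**Working it through.** The plan states no share of ET ratings affected, so there is no figure of its own to reproduce.

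**Inputs from the documents**
- Windows and targets: SAP Table 1.
- Scheduled visits: Weeks 2, 4, 8, 12, 16, 28, 40 and 52, within ±3 days (Visits 2–5) or ±7 days (Visits 6–8), counted from Baseline (SAP Appendix A).
- First dose on the day after Baseline (SAP 3.1). A visit exactly on schedule therefore falls on study day 7 × week, one day before the Table 1 target.
- HAMD-17, CGI-S, CSFQ-14 and KSS are rated at every scheduled visit. SDS is rated only at Weeks 4, 12, 28 and 52/ET (SAP 5.2.6).

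**Assumptions, not in the documents**
- ET days are uniform over study days 2–363 (362 days).
- All earlier scheduled visits are attended.

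Both are varied below.

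**Rule.** An ET rating is left out if an earlier scheduled rating lies in the same window and |ET day − target| > |scheduled day − target|. Equality keeps the ET rating.

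**Single case.** A Week 28 visit on day 196 gives |196 − 197| = 1. An ET rating on day 230 gives |230 − 197| = 33. The day-196 score is used, and the subject has no Week 40 value.

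**Day count for the four every-visit scales, visits on day 7 × week**

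| Window | Target | Visit day | ET days left out | Count |
|---|---|---|---|---|
| Week 2 | 15 | 14 | 17–21 | 5 |
| Week 4 | 29 | 28 | 31–42 | 12 |
| Week 8 | 57 | 56 | 59–70 | 12 |
| Week 12 | 85 | 84 | 87–98 | 12 |
| Week 16 | 113 | 112 | 115–154 | 40 |
| Week 28 | 197 | 196 | 199–238 | 40 |
| Week 40 | 281 | 280 | 283–322 | 40 |
| Week 52 (ET days 323–363) | 365 | – | none | 0 |

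Total: 5 + 3 × 12 + 3 × 40 = 161, and 161/362 = 44.5%.

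With visits exactly on target, each of the seven windows loses one more day: 161 + 7 = 168, and 168/362 = 46.4%.

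**Visits spread over their permitted days** (simulation, 200,000 ETs). An earlier scheduled visit shares the window for 48.3% of ETs, and the ET rating loses in 85% of those: 0.483 × 0.85 = 41.1%. In the other 15% the ET rating is selected.

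**Other assumptions, visits spread as above**
- Exponential ET times truncated at day 363: 34.7% (mean 60 days) to 41.4% (mean 365 days). The ET rating loses in 75–84% of shared windows.
- 85% visit attendance: 29.5% to 35.2% across the same timing assumptions.

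**Clustering of ET days** (visits on day 7 × week). ETs confined to days 2–154 give 81/153 = 52.9%. ETs confined to days 323–363 give 0/41. The 30–46% range therefore describes ET days spread over the whole period and is not a bound.

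**SDS.** Only the Week 4, 12 and 28 windows hold an earlier scheduled SDS that can compete.
- Visits on day 7 × week: 12 + 12 + 40 = 64, and 64/362 = 17.7%.
- Visits on target: 13 + 13 + 41 = 67, and 67/362 = 18.5%.
- Spread visits: 16.5%. Exponential ET times: 16.0–17.4%.

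These figures assume that an ET SDS in the Week 2, 8, 16 or 40 window is tabulated under that window. If the SDS table has only its scheduled rows, such ratings have no row. Those windows cover 20 + 28 + 56 + 84 = 188 days, giving (188 + 64)/362 = 252/362 = 69.6%. The SAP does not settle which reading applies.

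**The case against.** **The rule is coherent and little hangs on it.** Closest-to-target is a prespecified and sensible rule for by-visit tables. Efficacy is exploratory and descriptive, with no testing. The primary endpoint, treatment-emergent adverse events, is unaffected. Every rating is listed, and discontinuations are tabulated by reason (SAP 6). All of this stands and limits the consequence, but a listing is not a summary.

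**The laboratory row is an exception.** Vital signs (SAP 14.3) and ECG (SAP 14.4) have no last-value row either. That is correct. The laboratory row shows that the format is available, not that efficacy departs from a general pattern.

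**Other documents may deal with it.** Table specifications and programming conventions are separate and not available here. They could, but nothing in the SAP calls for such a row.

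**Stronger readings that the documents do not support**
- A reader might infer that an ET rating is dropped whenever a scheduled visit shares its window. SAP 5.3.2 compares distances and gives ties to the later rating, so ET ratings that are tied or closer are kept.
- A reader might take roughly 40% as the actual loss. The documents give neither ET dates nor attendance. An ET visit made in place of the next scheduled visit normally has no competitor and loses nothing. The figure also does not carry over to SDS.
- A reader might infer that the by-visit means are biased in favour of the drug. That follows only to the extent that subjects stopped because they worsened. Subjects discontinued because the sponsor stopped the study did not leave for that reason.

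**Conclusion.** The point holds in limited form. The plan as written leaves a complete ET efficacy rating out of all planned efficacy tables when an earlier scheduled rating in the same window is strictly closer to target.

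With uniform ET days over 2–363 and full attendance, the share is about 41–46% for HAMD-17, CGI-S, CSFQ-14 and KSS. It is about 30–46% once ET timing over that period and attendance are varied, and lower if ET visits stand in for scheduled visits or fall after day 322. For SDS it is about 16–19%, rising towards 70% if only scheduled SDS rows are shown. All of these shares rest on assumed ET timing.

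The effect on mean change has not been estimated, and its direction depends on why subjects stopped. This is a gap in reporting exploratory endpoints and does not affect the primary safety analysis. It is worth closing because the study stopped early and the remedy is cheap.

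**What to change.** In SAP 13, add one row labelled *last open-label assessment* to each efficacy table: HAMD-17 (with response and remission), CGI-S, SDS, CSFQ-14 and KSS. Define it as the last non-missing post-Baseline open-label value up to and including the EOT/ET visit, whether or not SAP 5.3.2 selected it for a window. The cut-off has to be written out because the SAP defines no on-treatment limit for efficacy ratings. Show the study day of that assessment alongside the row.

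Leave the by-visit rows unchanged. The new row does not alter the by-visit means; it puts the final ratings into a summary next to them. It also settles the SDS question, since the last SDS rating is then shown under either reading of the table rows.

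The cost is a sentence or two in the SAP and one row per table, with no new data. The downside is that the row pools subjects with different exposure times and must be labelled as doing so.
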